### **6.5.3 TMDS staff participants.**

*Inclusion criteria:*

1. Age 18 years and older.
2. TMDS staff member.

*Enrollment estimates:* Call center EMT enrollment is estimated to be 5 to 15. Driver enrollment is estimated to be 5 to 10. On-call physician enrollment is estimated to be 1 to 3.

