### **6.6.3 Parent/guardian participants not receiving a household visit**

For parent/guardian participants that are not receiving a household visit due to danger signs present, met capacity, or failed/declined delivery, a waiver of documentation of consent will be presented at the time of the initial call or at the time of the follow-up call (either 24-hour or at the 8-12-day follow-up call). The rationale for the waiver of documentation of consent is that the survey questions pose no more than minimal risk and written consent is not logistically feasible. Explanation of informed consent procedures may be obtained in English (official language of Ghana) or another locally spoken language (ex: Ga) in which the EMT obtaining consent and the participant providing consent are fluent as is common research practice in Ghana (see Gamada Letter of Support).

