### **6.6.4 TMDS staff participating in questionnaire/focus group**

A waiver of documentation of consent to participate will be obtained in English from MotoMeds staff members. The rational is that staff focus groups are likely to be performed over Zoom or a similar video-conferencing software.

[figure not shown]
**6.7 Workflow.** The call center will operate during the nighttime (exact hours will be determined from INACT1-G). Staffing will be elastic to the needs of the call center case volume. If there are multiple calls at one time, the call center will be staffed to field 1-2 calls at a time. If the call volume is greater than expected, the calls will be placed on hold until a call center EMT is available. If the delivery/household visit volume is greater than the capacity to respond, the contingency plan is as follows: A restriction ('cap') will be activated such that no more than 3 participants can be waiting for a delivery at one time. If there are more than 3 participants waiting, the participants will receive advice by phone and will not receive a delivery/household visit. These cases will be recorded as study data. If volume consistently exceeds the planned capacity, the number of staff (EMTs and drivers) will be increased as funding allows.

Call intake will be managed by the HIPAA-compliant call center software Twilio and case dispatch will be managed by the Beacon Crisis Response. Dispatch alerts via Beacon will include the caller's name, phone number, location, as well as patient complaints; Beacon is also HIPAA-compliant.

Severe cases, certain fever cases and cases with unsuccessful deliveries will be contacted by phone within 24 hours (maximum of 2 attempts over the course of another 24 hours) and all participants will be contacted (maximum of 3 attempts) at 8-12 days to ascertain disposition, if additional care was sought, and qualitative feedback about the service. Responses will be recorded on paper forms and/or directly into REDCap.

Focus groups with TMDS staff will be performed to determine service usability and acceptability from an operational perspective.

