## **6.10 Outcome Measures.**

**6.10.1 Aim I (clinical safety).** Establish rate of guideline adherence at the call center (primary outcome measure) and household. Determine sensitivity and specificity of each clinical variable using the in-person exam at the household as the reference standard. Establish congruence between call center and in-person assessment in terms of severity categorization, danger signs, disease type, and treatment. Determine clinical status at 8-12 days. Since evaluation of guideline adherence and congruence between the call center and household are part of the research question itself, and because clinical equipoise can exist beyond what can be reflected in written guidelines, small deviations from guidelines based on the clinical facts of the case are not considered protocol violations. Violations that led to an adverse or severe adverse effect will be reported as further specified in this study protocol.

**6.10.2 Aim II (feasibility from patient perspective).** Logistical data on patient workflow will be collected (duration of call, time to delivery). Parent/guardian feedback will be collected on the clinical, cost and quality aspects of the TMDS.

**6.10.3 Aim III (feasibility from staff perspective).** Domains of inquiry are clinical decision making, formulation of medications, communication with team members and households, and unanticipated opportunities for improvement.

**6.11 Data collection.** During the initial call, study staff will capture household contact information, details of the illness assessment and treatment recommendations from all callers meeting inclusion criteria. During the home visit the EMT will capture details of the in-person illness assessment and physical exam that includes anthropometric measurements (MUAC), vital signs, and/or RDT results. During the follow-up call, study staff will capture information on illness progression, outcome, and service feedback. During staff focus groups, a third party will capture staff opinions relating to service operations.

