**6.13 Staffing and Training.** The TMDS will be staffed by Ghanaian medical professionals including physicians and Advanced EMTs. On-call physicians with experience in pediatrics will provide supervision of guidelines and care. Consults will be flexible to mode of communication as to local standards of care; this may involve modes of communication beyond voice (e.g. images, video). If these modes are used, they will always occur with direct end-to-end encryption and they will not be saved nor used as research data. This flexibility prioritizes safety and yet respects protected health information. The staff will be trained on this distinction. All EMTs will have completed a minimum of 2 years of medical education at the NAS Paramedic and Emergency Care Training School or an equivalent institution. They will receive incoming calls, conduct phone assessments following standard of care guidelines, and make treatment recommendations. They will also perform consent and in-person assessments during home visits and will complete follow-up calls. Advanced EMTs will not make independent decisions but rather act within the scope of pre-defined clinical guidelines and/or consult on-call physicians. Trained local motorcycle taxi drivers will be contracted to deliver any needed medications, drive study EMTs to and from home visits. All staff members will be trained in occupational safety measures and human research protections. Staff members will receive training specific to this study, the clinical guidelines and study procedures by the PI and CIs and will undergo an assessment by the PI/CIs prior to being cleared for participation at the TMDS. They will receive on-going supervision by the PI/CIs and a NAS paramedic supervisor who completed paramedic-level training in the United States.

**6.14 Incentives.** No monetary benefits will be offered for participation in this study.

**6.15 Costs.** There is no cost for families to participate in this study and/or receive care.

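### The EMTs who treat children may also make those children's 8-12 day calls, so parent-reported status and service feedback are likely to read somewhat too favourably

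*Combined protocol and SAP*

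**What the plan says.** Section 6.13 (Staffing and Training) gives the EMTs the care role: "They will receive incoming calls, conduct phone assessments following standard of care guidelines, and make treatment recommendations". It then gives them the rest of the contact with the family: "They will also perform consent and in-person assessments during home visits and will complete follow-up calls".

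Section 6.11 (Data collection) describes what the later call yields: "During the follow-up call, study staff will capture information on illness progression, outcome, and service feedback". Section 6.7 (Workflow) adds that all participants are phoned "at 8-12 days to ascertain disposition, if additional care was sought, and qualitative feedback about the service".

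Section 5 lists clinical status at 8-12 days among the Aim I primary objectives, although it is not the primary outcome measure. It places parent/guardian feedback under Aim II.

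The size of the pool is in section 6.5.3: "Call center EMT enrollment is estimated to be 5 to 15".

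For the staff focus groups, section 6.11 plans separate capture: "During staff focus groups, a third party will capture staff opinions relating to service operations". No matching arrangement is described for families.

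**The concern.** One telephone call supplies both the 8-12 day clinical status and the family's view of the service. Both are verbal reports from a parent to a member of the service that gave free care, possibly to the person who examined the child. Parents tend to soften complaints to someone who helped them, and a provider has an interest in recording recovery. Both tendencies point the same way, toward a service that looks safe and acceptable.

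For many visited children this call is also the only scheduled contact after the visit. The 24-hour call in sections 6.7 and 6.8 covers only severe cases, some fever cases and unsuccessful deliveries. The limitations in section 6.19 do not mention the issue. At stake is the credibility of one Aim I objective and one Aim II outcome.

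**Working it through.** **Does the text name an independent caller?**

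- Section 6.13 assigns the follow-up calls to the EMTs.
- Section 6.11 says study staff capture the follow-up data, which might suggest someone else. But it uses the same term for the first call: "During the initial call, study staff will capture household contact information, details of the illness assessment and treatment recommendations". Section 6.13 has EMTs taking that call, so the term does not mark out an independent assessor.
- Section 6.6.3 fits this reading. For unvisited families the consent waiver may be presented at the initial call or "at the time of the follow-up call (either 24-hour or at the 8-12-day follow-up call"), and that section calls the person obtaining consent the EMT.
- No visible passage separates the caller from the treating EMT, limits what the caller sees, or compares answers by caller.

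**How often could caller and treating EMT coincide?**

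The plan gives no figure on this point. Its one precision figure, +/- 2.4% for guideline adherence in section 6.12, reproduces: 1.96 × sqrt(0.86 × 0.14 / 819) = 0.0238. It concerns an outcome that this point does not touch.

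Input: k = 5 to 15 EMTs (section 6.5.3). Assumption: each follow-up call goes at random to one of the k EMTs.

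| Child | EMTs involved | Formula | k = 15 | k = 5 |
|---|---|---|---|---|
| Visited, different EMTs for call and visit | 2 | 2/k | 2/15 = 13% | 2/5 = 40% |
| Visited, same EMT for both | 1 | 1/k | 1/15 = 7% | 1/5 = 20% |
| Not visited | 1 | 1/k | 1/15 = 7% | 1/5 = 20% |

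If staff tend to follow up their own cases the share is higher. If shift patterns separate them it is lower.

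**What could that do to a result?**

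This is an illustration only, since none of these values is in the documents. Let the true favourable proportion be t = 85%, and let a fraction f of unfavourable answers be recorded as favourable in affected calls. If a share s of calls is affected, the upward shift is s × (1 − t) × f.

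- All calls affected (s = 1), f = 10%, 20%, 30%: 0.15 × f = 1.5, 3.0, 4.5 points, giving 86.5%, 88.0%, 89.5%.
- Only same-EMT calls affected, visited children with two EMTs: from 2/15 × 0.15 × 0.10 = 0.2 points to 2/5 × 0.15 × 0.30 = 1.8 points.
- Only same-EMT calls affected, unvisited children: from 1/15 × 0.15 × 0.10 = 0.1 points to 1/5 × 0.15 × 0.30 = 0.9 points.

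For comparison, 819 enrolled less 10% lost (section 6.5.2) leaves 819 × 0.90 = 737 followed. At 86.5% to 89.5% the 95% half-width, 1.96 × sqrt(p(1 − p)/737), is 2.5 to 2.2 points. A larger sample would narrow the interval but leave the shift.

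**The case against.** The strongest reply is that little of consequence turns on these answers.

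- The primary outcome measure is call-center guideline adherence. That, the paired congruence analysis, call duration and time to delivery do not come from the 8-12 day call.
- The benchmarks in section 5 concern call duration and delivery time. No threshold is set for recovery or satisfaction.
- Section 7 requires immediate notification, leadership review and an on-site review or verbal autopsy for serious adverse events.
- This is a single-cohort pilot, so there is no allocation to conceal, and EMTs bring clinical skill to the call.
- On random assignment, 60-87% of calls to visited children would already come from an EMT not involved in that child's care.

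All of this stands, and it limits the point to non-serious status and service feedback. One qualification applies: section 7 works once an event is reported, and the follow-up call may be how it is first learned of.

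It is also fair that the data collection instruments cited in section 6.11 are not in the documents reviewed. Scripted questions or a caller field may already exist there. The third party at the staff focus groups is not described as a guard against bias, so it shows only that separate capture is planned elsewhere.

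Four stronger readings are tempting and are not supported:

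- A reader might infer that these outcomes are certainly biased. The direction is the expected one, but the documents give evidence on neither direction nor size.
- A reader might infer that the study's safety conclusion as a whole is compromised. The unaffected outcomes above rule that out.
- A reader might multiply 13-40% by the 737 followed children to get 98 to 295 same-EMT calls. The two-EMT fraction applies only to visited children, and the documents do not say how many enrolled children go unvisited.
- A reader might infer that the bias could never be checked afterwards. Section 6.11 allows clarification calls for up to 365 days, although no verification re-contact is planned.

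**Conclusion.** The point holds in limited form. The plan lets the EMT who took the call or made the visit also collect that child's 8-12 day answers, and non-serious parent-reported status and service feedback are likely to read somewhat too favourably as a result. The size is unknown.

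The scale figures of 13-40% for visited and 7-20% for unvisited children rest on two assumptions. Calls are assigned at random, and the section 6.5.3 estimate, which is for enrolment and not a nightly roster, describes the pool of callers. The 13-40% also needs different EMTs at the call and the visit.

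This is a worthwhile, inexpensive improvement to two outcomes, not a flaw in the primary analysis or the sample size.

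**What to change.** In sections 6.7 and 6.13, state that the 8-12 day call is made by an EMT or other existing staff member who neither took the initial call nor made the household visit for that child. The caller uses scripted status and feedback questions and sees only the contact, visit and consent status needed to make the call. Closing the record entirely would not work, because section 6.6.3 allows the consent waiver to be presented at that call.

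Record the caller's ID in REDCap. Report clinical status and feedback with any same-EMT calls shown separately. Add to section 6.19 that all callers remain service staff, so the bias is reduced but not removed.

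The cost is a roster rule, one data field and a sentence of limitation. No extra staff are needed, and care and sample size do not change. The downside is some rostering constraint when few EMTs are on shift.

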### **6.18 Data Analysis**

Data will be aggregated with REDCap and analyzed in R. Statistical support will be provided by the UF Clinical and Translational Science Institute.

Quantitative data will be analyzed using frequentist statistics, which will include using proportions for categorical variables, median and interquartile ranges for quantitative variables, effect size, sensitivity/specificity calculations, interrater agreement (e.g. Cohen's kappa). Qualitative data will be transcribed, coded to evaluate themes, and summarized to identify opportunities for improvement.

### **6.19 Limitations**

*Low sample size.* Household visits at nighttime are logistically challenging, therefore the study area must be limited in size to ensure safety and efficiency. The size of the study area dictates the population eligible for enrollment. Prior to commencing the intervention, it is difficult to assess whether the designated study area will provide adequate call volume to reach enrollment. We will address this limitation through active advertisement.

*Enrollment biases.* The intervention is intended to provide pre-emergency care to children who are experiencing a health problem during nighttime hours. Due to the lack of affordable, qualified healthcare options in the study area, households who could potentially visit a health center during the day may wait until nighttime to take advantage of the call center service. This could bias our understanding of the nighttime healthcare needs and call center functionality.

*Geographic bias.* The call center will be advertised as a service for households in a specific geographic area. In Ghana, boundaries at the community level (US equivalent to neighborhoods) are not officially defined and the address system is based on proximity to landmarks. As a result, it is possible that some callers outside of the study area could be enrolled or some callers inside the study area could be excluded, although the former is more likely to occur. While a 'fuzzy radius' impacts logistics, we do not anticipate this to impact the primary outcomes.

*Limited scope.* The study is designed to evaluate congruence of phone vs in-person assessments for non-emergent patients. Emergent patients will be advised to seek care immediately. The exclusion of emergency patients limits the scope and generalizability of the study to the full spectrum of EMS services. In-person data on emergent patients will not be obtained in this study.

*Limited diagnostic ability.* The study is designed to provide acute care at the community level; thus, it is not possible for gold standard diagnostics such as microscopy and PCR to directly inform individual treatment plans. For malaria, in lieu of microscopy, point-of-care rapid diagnostic testing may be used for diagnosis.

---

## **7. Data Safety Monitoring Committee**

---

Similar to the iteration of this study that was conducted in Haiti, this study is considered minimal risk and a DSMC is not required, unless instructed by the IRB.

A Medical Advisory Committee consisting of Ghanaian and University of Florida physicians specializing in emergency medicine, prehospital medicine, infectious disease, and pediatrics will be convened. The Medical Advisory Committee will receive biweekly email updates including case summaries and relevant medical questions for discussion.

Severe adverse events will be reported per protocols of the Ghana Health Service Ethics Review Committee and the UF IRB. SAE will be defined as: Any event that results in death, significant disability, incapacity, and/or life-threatening situation that developed after enrollment of any patient within the enrollment period (enrollment to the 8-12 day follow-up call). In the event of an SAE, the paramedic supervisor, on-call physicians (primary and secondary), and study director will be notified immediately. NAS leadership and UF leadership (PIs) will be notified the following morning. The leadership will review the situation, dispatch a team to conduct an on-site review/verbal autopsy of the case, and notify the clinical advisory committee. A verbal report will be made to the Ghana IRB within 3 days per their requirements. A preliminary written report will be submitted to both the Ghana IRB and the USA (UF) IRB within five days, as well as the clinical advisory committee. After IRB review and recommendations, a final report will be submitted. The study will continue, be amended, suspended or terminated based on this review process. Given high rates of morbidity and mortality among the participant population and prior research that found the mortality rate in an INACT2 TMDS model in Haiti to be one in 391 participants (0.2%), we anticipate in a population of 891 enrollment participants there will be two mortalities. The threshold for suspending the study for review will be 2 mortalities per two hundred patients enrolled (1%).

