## **8. Possible Discomforts and Risks**

### *Discomforts and risks.*

1. Breach of confidentiality.
2. Caller may underestimate severity of symptoms. A caller may underestimate the severity of a patient's symptoms, either intentionally or unintentionally, leading to an enrollment that does not meet inclusion criteria. This may result in a delay of seeking immediate care for a true emergency.
3. Financial cost. Seeking care at night at established health facilities is expensive. If we conservatively recommend seeking emergency care but the patient does not have an emergency, this will create unnecessary financial burden for the family.

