### *Efforts to minimize risk.*

1. To address risk of breach of confidentiality, paper-based data collection will be minimized and when possible, secure electronic-based data collection tools will be used (REDCap). All staff will be trained in the protections of personal information as well as protections of human subjects research. All paper-based documents will

be maintained in a locked cabinet in a secure building with keyed-access limited to study leadership.

2. To minimize understating disease severity, the guidelines for diverting callers directly to a healthcare facility will adhere to established guidelines (e.g. WHO IMCI). The approach will draw on best practices to interrogate callers and have scripts that ask clear dichotomous questions. The study data will be monitored to determine the concordance between phone and household assessments.
3. When directing callers to seek immediate care at a medical facility, study staff will be clear that they are providing qualified recommendations based on the relayed information, but the final decision is the responsibility of the family. Given the conservative approach, we acknowledge that a small percentage of families may experience unnecessary cost exposure which is weighed against the benefit of likely reducing overall morbidity and mortality.

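### The SAE definition omits hospital admission and is unclear for emergencies already present at the call, so a missed emergency that the child survives may escape expedited reporting, and no other review route has a trigger for it

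*Combined protocol and SAP*

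**What the plan says.** Section 7 gives the study's own SAE definition: "Any event that results in death, significant disability, incapacity, and/or life-threatening situation that developed after enrollment of any patient", with the window "within the enrollment period (enrollment to the 8-12 day follow-up call". The list contains death, disability, incapacity and a life-threatening situation. Hospital admission is not in it, and no other section makes admission reportable. The section also says "Severe adverse events will be reported per protocols of the Ghana Health Service Ethics Review Committee and the UF IRB"; those rules are not reproduced. An SAE sets off immediate notification, a leadership and on-site review, and ethics reports (verbal within three days to the Ghana body, written within five days to both). After that review the study may go on, be changed, be paused or be ended. One numeric suspension threshold is stated: two deaths per 200 enrolled.

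Section 8 lists three risks: a confidentiality breach, a caller who understates severity, and unnecessary cost. Of the second it says "This may result in a delay of seeking immediate care for a true emergency". The stated mitigation includes "The study data will be monitored to determine the concordance between phone and household assessments".

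Three other provisions bear on the point:
- Section 7: "The Medical Advisory Committee will receive biweekly email updates including case summaries and relevant medical questions for discussion".
- Section 6.10.1: "Violations that led to an adverse or severe adverse effect will be reported as further specified in this study protocol". The same section makes call-center/household congruence on severity and danger signs an Aim I measure.
- Section 6.7: the 8-12 day call is made "to ascertain disposition, if additional care was sought, and qualitative feedback about the service".

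**The concern.** Of the three risks in section 8, understated severity is the only clinical one. It concerns a child who is already an emergency but enters the study as mild or moderate. The SAE definition turns on what arises after enrollment and leaves out admission, which is how many survived emergencies would show themselves. If such cases fall outside the definition, the expedited pathway need not start. There is no data safety monitoring committee unless the IRB asks for one, so what remains is general oversight with no stated point at which repeated under-triage must be escalated. Clinical safety is Aim I, so this is a signal the study should be able to act on while it is running.

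**Working it through.** The question is mainly one of wording, so the first three steps set the provisions side by side.

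**1. Apply the definition to an under-triaged child.**
- Stable at the call, life-threatened later because care was delayed: an SAE.
- Already life-threatened at the call, then dies or is left disabled or incapacitated: an SAE, because that outcome arises after enrollment.
- Already life-threatened at the call, survives without disability or incapacity: doubtful. The timing qualifier may govern every listed item or only the last, but on both readings it governs the life-threatening category. Read literally, this child is excluded.
- Admitted, recovers, never classed as life-threatened: outside the definition on any reading.

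**2. When enrollment starts.** Under section 6.6.3, a caregiver whose child gets no household visit may be offered the consent waiver at the first call, the 24-hour call or the 8-12 day call. If enrollment is dated from consent, the SAE window could open at the contact that closes it. The plan does not say which date applies.

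**3. Do the other routes set a count, a trigger or an escalation?**
- Biweekly updates: recipient and frequency are given. Required content beyond summaries and questions, a running count and a trigger are not.
- Concordance monitoring (section 8): no frequency, recipient, threshold or action is given, and section 7 does not mention it.
- Harmful violations (section 6.10.1): an EMT who is told a milder story can follow the guideline exactly, so the hazard need not involve a violation.
- Congruence (section 6.10.1): an outcome measure, with no interim look specified.
- 24-hour call (section 6.7): made for severe cases, certain fever cases and unsuccessful deliveries. A child over the delivery cap who is in none of these groups gets no visit and may next be contacted at 8-12 days.

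**4. The death-based threshold.** The plan's own figure reproduces. Expected deaths = N × 1/391:
- N = 891 (as printed in section 7): 2.28, consistent with the stated two.
- N = 819 (minimum enrollment, section 6.5.2): 2.09.
- N = 1365 (maximum): 3.49.

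For a single block of 200, the chance of two or more deaths is 1 − (1 − p)^200 − 200p(1 − p)^199:
- p = 1/391: 9.4%.
- p = 1%: 59.5%.

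So even at a true mortality of 1%, about four times 1/391, one block of 200 misses the threshold about 40% of the time. The plan does not say whether the count is by block or cumulative; the block is my assumption. These figures show only that deaths are a sparse signal. They neither prove nor disprove the wording gap.

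**5. Size of the gap.** The documents give no rate of missed emergencies. Under an assumed 0.5% to 5%, the formula gives 819 × 0.005 = 4 to 819 × 0.05 = 41. But 819 is total minimum enrollment and includes children who get no visit (section 6.6.3), so it is the wrong base for danger signs found at a visit. On the right base, the same assumption means 0.5 to 5 per 100 visits completed. Both are illustrations, not estimates.

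**The case against.** The strongest reply is that the plan has more safety review than the SAE list suggests. A reader might infer that a missed emergency gets no report or review unless the child dies or is disabled. The documents do not support that. Incapacity and life-threatening deterioration after enrollment are listed, and harm through delay often takes the second form. Case summaries reach a physician committee every two weeks and are not limited to SAEs. Concordance is to be monitored for this very risk, and on-call physicians and investigators supervise throughout (section 6.13).

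A reader might also infer that only deaths can pause the study. That is wrong too: any SAE review may end in suspension, and the two-per-200 rule is merely the only numeric threshold. Nor can it be said that the hazard would surface only at final analysis.

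The design also protects the individual child. Delivered cases are meant to be examined before medication is handed over, against a delivery benchmark under two hours, and a danger sign found then leads to advice to seek care and an offer of ambulance referral. The two ethics bodies' own SAE rules might add admission; that cannot be checked from the documents.

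All of this stands, and it narrows the point. It does not close it. Care for one child is not a signal across children, none of the general routes says what number of missed danger signs or admissions calls for action, and staff will work from the definition printed in section 7. It is also fair that a danger sign at the visit may have appeared after the call, so not every discordance is a missed emergency.

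**Conclusion.** The point holds in a limited form. What is missing is required expedited reporting of one class of event, and a defined trigger for it in the other review routes; review as such is not missing. The class is the under-triaged child who survives without disability or incapacity and who either was already life-threatened at the call or was admitted without being classed as life-threatened. For admission, the omission is plain on the text. For emergencies present at the call, the exclusion is a natural reading of an ambiguous clause, made less certain by the undefined start of enrollment.

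The conclusion assumes that the definition in section 7 is applied as written and that the ethics bodies' rules do not widen it. Its size in children cannot be given. It should be settled before enrollment because the remedy is cheap and bears directly on Aim I.

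**What to change.** In section 7:
- State that a life-threatening event counts as an SAE whether or not the condition predated enrollment.
- Add a reportable safety event, separate from the SAE pathway: any child triaged mild or moderate by phone who has a danger sign at the household visit (or at the 24-hour call where one is made), or who is reported admitted to hospital by the 8-12 day call.
- Record admission as an explicit item in the follow-up questions on disposition and further care. The documents do not show it as a field now.
- Put each case and the running counts in the existing biweekly committee update. For danger signs at the visit, the denominator is household visits completed. For admissions it is follow-up calls completed: with the planned 10% loss, about 819 × 0.9 = 737 at minimum enrollment.
- Have the committee set, before the first enrollment, the count or rate that prompts leadership review.

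Referral and treatment rules stay as they are. The cost is protocol wording, one follow-up item and a tally line in an existing email. The downside is a few more events to review, some of them changes between call and visit rather than missed emergencies. Sending them to the advisory committee instead of through on-site review keeps that load small.
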